Profile of Mood States Abbreviated [21]. Participants are presented with a list of 40 words that describe feelings people have. They are asked to circle the number that best describes how they feel right now from 0 (not at all), 1 (a little), 2 (moderately), 3 (quite a lot) to 4 (extremely). Alogue scales - . A Total Mood Disturbance score (TMD) is also calculated by summing the totals for the negative subscales (Tension, Depression, Anger, Fatigue, Confusion), and subtracting the totals for the positive scales (Vigour, Esteem-related Affect [Note that 2 item are reverse scored for the ERA subscale]). See Appendix 3. The primary outcome measure is the TMD, but we will conduct secondary analyses to examine the effects of the interventions on the subscale scores.

Modified Auckland Sleep Questionnaire [22]. The Auckland Sleep questionnaire was developed to diagnose common sleep disorders in primary care. We will use the items about current sleep and asked participants to rate them in reference to the previous week (rather than the previous month as in the original questionnaire). The overall sleep quality rating will be used in the analysis (Appendix 4).

Visual Analogue Scales

To assess the acute effects of the intervention, participants will be asked to complete ratings of overall mood, relaxation, and stress before and after one session each week. Participants are asked to rate how they are feeling *right now* using a visual analogue scale (VAS) from 0 (worst I've ever felt not relaxed, not stressed,) to 100 (very stressed, very relaxed, best I've ever felt)[23, 24] see Appendix 5.

e) Objectives

Primary Objective

To determine if the effects of listening to singing bowl music are equivalent to that of progressive guided muscle relaxation on self-report measures of mood in young adults (Total Mood Disturbance of the POMS) at 4- and 8- weeks post intervention.

Secondary Objectives

To compare the effects of the interventions on:

- Profile of Mood States-Abbreviated (POMS) subscale scores
- Overall sleep quality from the Auckland Sleep Questionnaire
- VAS ratings of mood, stress and relaxation

Exploratory analyses will be undertaken to determine i) how frequently the participants use the interventions in weeks 4-8, and ii) the acceptability of the interventions.

4. Study population

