A previous study examining the effects of an in person Tibetan singing bowl (n=62) session showed mean reductions of 0.49 to 1.23 (SD 0.19-1.05) in five POMS subscale scores [16]. A study with a much smaller group of teenage males (n= 11) showed significant reductions in POMS depression scores post-intervention [19]. In person PMR or Autogenic relaxation sessions in young soccer players (n=8) produced significant reductions in four of the six POMS-A subscales (mean difference 2.13 to 4.25; SD 2.38 to 4.47) [25]. As the current study is online rather than in-person, and the sessions are shorter, the effects may be somewhat smaller. Given this we are aiming to recruit a minimum of 100 participants (50 per group). This will provide > 90% power (2-sided $\alpha=0.05$) to detect a medium size effect of the intervention on the POMS subscales.

Analysis Plan

Univariate repeated measures ANOVA will be used to examine the effects of the intervention on the overall TMD score from the POMS, VAS scores and sleep scores. Repeated measures MANOVA will be used to examine changes in the POMS subscale scores.

Participants will be excluded from the analyses if they have not completed at least one intervention session per week for the first four weeks. The number of sessions completed during the first four weeks may be included as a covariate in the analyses.

7. Safety Concerns

Participants will be encouraged to contact us if they have any concerns. We will discuss the issue with the clinical advisor (with the participants consent) and encourage the participants seek support from their GP in the first instance. We will also have a list of support organisations available for participants.

8. Publication

All listed investigators will be co-authors on any presentation or manuscript published from this study. The principal investigators will be the first authors on the study manuscript.

9. References

1. Health Mo. Annual Data Explorer 2022/23: New Zealand Health Survey [Data File]. 2023.

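### The stated >90% power is tied to no contrast or effect metric; for a medium (0.5 SD of the analysed score) SB-versus-PMR difference on one subscale, 50 per group gives about 70%

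*Combined protocol and SAP*

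**What the plan says.** Section 6, Sample size, sets a minimum of 100 participants, 50 per group, and continues: "This will provide > 90% power" at a two-sided 5% level, "to detect a medium size effect of the intervention on the POMS subscales". It gives no numerical effect size, contrast, SD, correlation between occasions or formula.

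The planning evidence in the same paragraph consists of reductions. An in-person singing-bowl study of 62 people "showed mean reductions of 0.49 to 1.23 (SD 0.19-1.05) in five POMS subscale scores"; the background section describes its design as pretest-post-test. A study of 11 teenage males is cited for reduced depression scores. A relaxation study in eight soccer players is cited for reductions on four subscales ("mean difference 2.13 to 4.25; SD 2.38 to 4.47"). No difference between two treatments is quoted. The paragraph adds that effects here may be smaller, because sessions are online and shorter.

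The trial randomises SB against PMR (section 5), with no untreated arm. For the subscales, the secondary objective (section 3e) is "To compare the effects of the interventions on" those scores. The Analysis Plan assigns the subscales to repeated measures MANOVA, and TMD, VAS and sleep to univariate repeated measures ANOVA. It removes participants who fall short of a weekly session during the first four weeks. No loss rate or inflation is given.

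**The concern.** Randomisation supports one inference, SB versus PMR, so a reader will take the power statement as applying to it. The evidence offered concerns change after a session, which is a different quantity. If both arms improve by similar amounts, each can show a clear before-after change while the difference between them stays small.

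The consequence lies in interpretation. The hypothesis (section 3a) is that the two interventions do equally well, so a non-significant subscale comparison is likely to be read as support. With power above 90%, that result would miss a medium difference less than one time in ten. With 70%, it would miss it about three times in ten.

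This point is confined to whether the figure is right for its own stated target, the subscales. Which endpoint should be powered is a separate matter.

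**Working it through.** **Inputs.** From section 6: 50 per group, two-sided 5%, power above 90%, a medium effect. Assumptions, because the plan gives no values: medium is d = 0.5 for a comparison of means or f = 0.25 for ANOVA; the correlation ρ between occasions is shown over a range; losses are illustrated at 10%, 20% and 30%. Power is from the noncentral t or F distribution.

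**1. Reproducing the plan's figure.**
- *Change within one arm.* Noncentrality d√n = 0.5 × √50 = 3.54, 49 df: power **93.4%**.
- *Group-by-time interaction, f = 0.25, N = 100, two occasions.* λ = f² × N × 2/(1 − ρ) = 12.5/(1 − ρ): power 93.8% at ρ = 0 and 99.9% at ρ = 0.5. With three occasions it is 97.7% at ρ = 0 and higher above that.

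Both agree with the stated >90%. In a 2 × 2 layout, f equals the difference between the arms' changes divided by 4 SD. So f = 0.25 means a difference of 4 × 0.25 = **1.0 raw SD**. A difference of 0.5 raw SD is f = 0.125, with power 55% at ρ = 0.3, 70% at 0.5 and 79% at 0.6.

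**2. SB versus PMR, 0.5 SD of the analysed score.** Noncentrality d√(n/2) = 0.5 × √25 = 2.50, 98 df: power **69.7%**.
- For 90% at 50 per arm: 0.65 SD gives 89.6% and 0.66 SD gives 90.4%.
- For 90% at 0.5 SD: 86 per arm.

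**3. SB versus PMR, 0.5 raw SD at one follow-up, 50 per arm.** The standardised difference is 0.5/√(2(1 − ρ)) for change scores and 0.5/√(1 − ρ²) with baseline adjustment.

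| ρ | Change score: d | Power | Baseline-adjusted: d | Power |
|---|---|---|---|---|
| 0.3 | 0.423 | 55% | 0.524 | 74% |
| 0.5 | 0.500 | 70% | 0.577 | 82% |
| 0.6 | 0.559 | 79% | 0.625 | 87% |
| 0.65 | 0.598 | 84% | 0.658 | 90% |
| 0.7 | 0.645 | 89% | 0.700 | 93% |

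So 90% is reached at ρ of about 0.65 with baseline adjustment and slightly above 0.7 with change scores.

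**4. Repeated measures ANOVA on all three occasions.** Take no difference at baseline and 0.5 raw SD at both follow-ups, with equal correlations. The centred sum of squares is 2 × 0.25 − 1/3 = 0.167, and λ = 0.167 × 25/(1 − ρ). Power of the interaction test is 57% at ρ = 0.3, 73% at 0.5 and 92% at 0.7.

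**5. After exclusions.** Repeating step 2 with 45, 40 or 35 analysed per arm (10%, 20% or 30% lost) gives 65%, 60% or 54%.

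**The case against.** A reader might infer that >90% can arise only from a within-arm calculation, or that the sponsor ran a paired calculation by mistake. The documents support neither. Step 1 shows that an interaction at f = 0.25, a conventional medium value for the ANOVA family that the plan names, also gives >90%, so no arithmetic error is shown. The paired origin is suggested by ratios such as 0.49/1.05 = 0.47 and 2.13/4.47 = 0.48. Those pair the smallest mean with the largest SD from separate ranges that need not belong to the same subscale; another pairing gives 0.49/0.19 = 2.6. The plan does not say whether the SDs are of changes or of scores.

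The 70% is also not universal. A high correlation raises it (step 3). If baseline is adjusted for and the 4- and 8-week scores are averaged, the standardised difference is 0.5/√((1 + ρ)/2 − ρ²). Power is then 91% at ρ = 0.3 and 94% at ρ = 0.5, given equal correlations and the same difference at both times. That analysis is not in the plan, which calculates separate differences from baseline and names repeated measures ANOVA or MANOVA.

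Finally, the subscales go to MANOVA, and the figures above are univariate. As an illustration, take Hotelling's T² on seven change scores, 50 per arm, with a common correlation among subscales of 0.2 to 0.6. Power falls from 90% to 55% if all seven differ by 0.5 SD, and rises from 42% to 74% if only one does. So 70% is an illustrative univariate figure and not the power of the planned test.

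These objections limit the wording. They do not make >90% correct for a 0.5 SD between-arm difference without assumptions that the plan leaves out.

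**Conclusion.** The concern holds in limited form: the statement is under-specified, and read as power for a medium SB-versus-PMR difference it is too high. The gap is about 70% against >90%, or about a 30% chance of missing the difference instead of under 10%, before any exclusions. This rests on medium meaning 0.5 SD of the analysed score, a univariate two-sided 5% comparison and 50 analysed per arm. If 0.5 is in raw SD units, the result depends on a correlation that the documents do not state. The interaction reading does not close the gap, because it reaches >90% by assuming a difference twice as large. How the sponsor obtained the figure cannot be determined from the documents.

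**What to change.** Replace the power sentence with: *With 50 analysed per group, a univariate SB-versus-PMR comparison of one subscale (two-sided 5%) has about 70% power for a difference of 0.5 SD of the analysed score and 90% power for about 0.66 SD; if the adherence exclusion leaves 45, 40 or 35 per group, power for 0.5 SD is about 65%, 60% or 54%.*

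Add two notes. The planned MANOVA has a different power, which depends on the correlations among subscales. The cited studies are quoted as reductions only, with no between-treatment difference.

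Keep >90% only if the sponsor states the contrast, effect metric and correlation that produce it. The text should not assert that it came from a paired calculation unless the sponsor confirms this.

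The cost is one reworded paragraph and a less favourable stated power. Recruitment need not change, provided that the analysed numbers are reported as they fall and the minimum of 100 is not presented as 50 analysed per group.

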Taken together these findings suggest that relaxation music played on singing bowls may be beneficial in improving mood, decreasing stress, and improving sleep. Extending the previous work by co-PI [name] [19], this study seeks to compare the effects of listening to quartz crystal singing bowl music with guided relaxation on mood, stress and sleep in a larger sample of young adults. Participants will be randomly assigned to either the singing bowl (SB) or guided progressive muscle relaxation (PMR) condition. Participants will be asked to listen to singing bowl music or complete the PMR exercises for 10 minutes three time a week for four weeks (delivered online via the Qualtrics platform) and will then be given free access to the music or guided meditation for another four weeks whilst their use is monitored. Ratings of mood, stress and sleep will be completed at baseline, 4 weeks and 8 weeks. For one session per week, participants will be asked to complete visual analogue rating scales of their mood/stress immediately before and after the session to determine the acute effects of the intervention.

3. Study Design and Method

a) Hypothesis

Listening to singing bowl music will result in equivalent improvements in mood, stress and sleep compared with guided relaxation immediately after the session, and at 4- and 8-weeks post-intervention.

b) Design

Randomised controlled trial.

c) Intervention

Singing bowl music (SB)

The singing bowl relaxation music ('Tranquility' available on Spotify) was played by [name] and professionally recorded. The sound is produced by tapping the bowls and rubbing them with a rubber mallet. Each session took approximately 10 minutes.

Guided relaxation (PMR)

A guided progressive muscle relaxation audio (recorded by the NZ Cancer Society <https://www.youtube.com/watch?v=Zydrp3rfJdY>) and similar to the PMR script from the Anxiety and Phobia Workbook by Edmund Bourne [20]) was used. The session took approximately 12 minutes. Participants were instructed to start by sitting or lying comfortably, taking some deep breaths and then tense and relax muscles in a sequential manner from the head to the feet (see Appendix 6 for an example of the PMR script).

d) Outcome measures

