Members of the general population aged 16-25 years will be recruited to participate in the study. To be eligible to take part, potential participants need to have good hearing, good understanding of English and have a mobile phone or computer to access the intervention and questionnaires via the Qualtrics application. Participants will be excluded if: they are regular users of relaxation music from quartz crystal singing bowls or progressive muscle relaxation, have an untreated mental health diagnosis, or are receiving treatment from a psychologist or psychiatrist. (See Appendix 1 for the eligibility questionnaire).

Participants will initially be recruited from the first-year psychology participant research pool (IPRP) and will receive up to 10% course credit for participation (as outlined in the flyer and participant information sheet (PIS) appendices 7 and 8. Study flyers will also be posted around the University to recruit more widely (participants can choose to enter a prize draw). In the next stage of the study, we will approach secondary schools to advertise the research to their students (subject to additional ethics approval).

We aim to recruit at least 100 participants, with a minimum of 50 university students.

5. Study Procedures

The study/questionnaires will be delivered via the Qualtrics software. Those interested in participating will contact the researchers via a study email address [contact]. Each participant will be allocated to one of the students who will be responsible for monitoring the participant's completion of the questionnaires and sending reminders to complete the intervention as needed. Participants will be sent an individual link to the information sheet, consent form, and eligibility form (Appendices 1, 8). Those meeting the eligibility criteria will automatically be directed to complete the demographic questionnaire (Appendix 2), and the mood (POMS) and sleep measures (modified Auckland Sleep questionnaire) Appendix 3 & 4, (T1).

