Participants will then be randomised to either the singing bowl (SB) (Tranquility by [name]) or the guided relaxation group (PMR; example script is in Appendix 6) and given access to the relevant audio on the qualtrics platform (to allow us to monitor when and for how long participants engaged with the intervention). Participants will be asked to listen to the relevant intervention 3 times a week for four weeks (each session is approximately 10 minutes). Before and after one session each week, participants will be asked to complete the visual analogue ratings scales to assess the acute effects of the intervention on their mood, stress and relaxation (Appendix 5). Participants will be sent reminders 3 x per week to complete the intervention.

Participants will be asked to complete the mood and sleep measures again after 4- (T2) and 8-weeks (T3)

The students will actively monitor participant's engagement in the study and send email reminders to complete the intervention sessions (Qualtrics is set up to automatically send email notifications to the study email address when participants complete each session so we can keep track of where they are up to) and the questionnaires at 4 and 8 weeks after the start of the study. After the first four weeks, participants will have free access to either the SB or PMR audio to use as much as they like, and we will monitor the frequency of use via the qualtrics app for the next four weeks. We will send out the link to the intervention weekly in weeks 4-8.

After completion of the 8 week questionnaire (T3) participants will be provided unlimited (and unmonitored) access to both audio tracks and will be asked to provide any feedback on the study.

6. Statistical Analysis

Primary outcomes

Difference scores between baseline (T1) and T2 (4 weeks), and T3 (8 weeks) for the POMS TMD will be calculated.

Secondary outcomes

- a) Difference scores between baseline (T1) and T2 (4 weeks), and T3 (8 weeks) for the POMS subscale scores and Auckland Sleep questionnaire will be calculated.
- b) The number of intervention sessions completed between T1 and T2, and T2 and T3.
- c) Feedback on the acceptability and effectiveness of each intervention.

Sample size

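### The primary objective is equivalence on POMS TMD, but the only planned TMD analysis tests for a difference and no margin or confidence-interval rule is given

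*Combined protocol and SAP*

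**What the plan says.** The hypothesis in section 3(a) reads "Listening to singing bowl music will result in equivalent improvements in mood, stress and sleep compared with guided relaxation". It covers both the acute effect of a session and the two follow-up visits. The primary objective in section 3(e) is "To determine if the effects of listening to singing bowl music are equivalent to that of progressive guided muscle relaxation", measured by POMS TMD at 4 and 8 weeks.

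Section 6 deals with TMD in two places. Under Primary outcomes: "Difference scores between baseline (T1) and T2 (4 weeks), and T3 (8 weeks) for the POMS TMD will be calculated". No test or decision rule is attached to those scores. Under Analysis Plan: "Univariate repeated measures ANOVA will be used to examine the effects of the intervention on the overall TMD score from the POMS". The factors, the contrast of interest and the criterion for a conclusion are not given.

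The sample size paragraph justifies 50 per group by more than 90% power, at two-sided alpha 0.05, "to detect a medium size effect of the intervention on the POMS subscales". No section available for review states an equivalence margin, a two one-sided tests procedure or a confidence-interval rule, or says whether equivalence must hold at one time or both. Non-inferiority appears only in the title of a reference cited for the visual analogue scales.

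**The concern.** The null hypothesis of a repeated measures ANOVA is that the arms do not differ. A significant result would count against equivalence. A non-significant result is inconclusive, because it can come from similar effects or from too little information. The analysis therefore has no outcome that validly supports the primary objective.

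The incentive also runs the wrong way: the fewer participants analysed, the more likely the hoped-for non-significant result. This matters here because the Analysis Plan removes non-adherent participants ("Participants will be excluded from the analyses if they have not completed at least one intervention session per week for the first four weeks") and the sample size makes no allowance for dropout. A report of equivalence could follow from a real between-arm difference that the trial was too imprecise to detect.

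**Working it through.** **1. The plan's own figure.** Inputs from section 6, Sample size: 50 per group, two-sided alpha 0.05, power above 90%, a medium effect with no number given. I assume d = 0.5 or f = 0.25.

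- Between-arm difference, d = 0.5: Φ(0.5·√(50/2) − 1.96) = Φ(0.54) = 0.705 (exact t: 0.697). This does not reach 90%, which would need 85 per arm.
- Pre-post change within one arm, d = 0.5, n = 50: 0.934.
- Group-by-time in a repeated measures ANOVA, f = 0.25, N = 100, m = 2 or 3 visits, λ = f²·N·m/(1 − ρ), ρ from 0 to 0.7: 0.938 to above 0.999.
- Between-group main effect, f = 0.25, λ = f²·N·m/(1 + (m − 1)ρ), ρ from 0.3 to 0.7: 0.77 to 0.92.

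The stated figure can be reached under the second and third readings. Every reading gives power to detect a difference or a change. None gives power to show equivalence, and the plan's figure concerns subscales, not TMD.

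**2. How often a real difference would be non-significant.** The plan gives no TMD SD, correlation, margin or dropout figure, so these are assumptions: raw SD 1, equal correlation ρ between visits, the same shift at T2 and T3, no missing data, and the ANOVA read as group-by-time over T1–T3 at alpha 0.05. There were 40,000 simulated trials per cell. The 35 per arm is an assumed analysed number.

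| Analysed per arm | True difference | ρ = 0.5 | ρ = 0.6 | ρ = 0.7 |
|---|---|---|---|---|
| 50 | 0.5 SD | 28% | 17% | 8% |
| 50 | 0.3 SD | 68% | 61% | 50% |
| 35 | 0.5 SD | 44% | 34% | 21% |
| 35 | 0.3 SD | 77% | 72% | 64% |

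With no true difference the test was non-significant 94.9–95.1% of the time, as it should be. As a cross-check, an exact two-sample t-test with SD 1 and 50 per arm is non-significant 30% of the time at 0.5 SD and 68% at 0.3 SD.

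**3. Precision at one time.** The between-arm difference has SD √(2(1 − ρ)) for change scores and √(1 − ρ²) after baseline adjustment. The 90% half-width is t(0.95; 2n − 2)·SD·√(2/n).

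| Per arm | Estimate | ρ = 0.5 | ρ = 0.6 | ρ = 0.7 |
|---|---|---|---|---|
| 50 | change | 0.332 | 0.297 | 0.257 |
| 50 | adjusted | 0.288 | 0.266 | 0.237 |
| 35 | change | 0.399 | 0.357 | 0.309 |
| 35 | adjusted | 0.345 | 0.319 | 0.285 |

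**4. Power to show equivalence.** Equivalence is declared if the 90% interval lies inside ± margin, which is two one-sided tests at 0.05. The true difference is 0. Approximately, power = 2Φ(margin/SE − 1.645) − 1. For change scores at ρ = 0.5, n = 50 and margin 0.5: SE = √(2/50) = 0.2, giving 2Φ(2.5 − 1.645) − 1 = 0.61 (0.598 with the t distribution). Ranges below run over ρ = 0.5 to 0.7. One-time values are by numerical integration and both-times values by simulation.

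| Per arm | Margin | Times required | Change scores | Baseline-adjusted |
|---|---|---|---|---|
| 50 | ±0.5 SD | one | 60–88% | 78–93% |
| 50 | ±0.5 SD | both | 39–79% | 61–87% |
| 50 | ±0.4 SD | both | 9–44% | 24–56% |
| 50 | ±0.3 SD | both | 0–6% | 1–12% |
| 35 | ±0.5 SD | both | 13–52% | 30–63% |

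**The case against.** The plan never says that a non-significant ANOVA will be read as equivalence. The planned data could also yield a between-arm estimate and interval. Elsewhere the document reads like an ordinary comparison: the background and the secondary objectives speak of comparing effects, and the sample size is set to detect an effect. The word *equivalent* may simply be loose. The numerical illustration rests on assumed inputs, and its range is too wide to show that 50 per arm is too few.

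Much of this is fair, and none of it removes the problem. What is missing is the pre-specified criterion, and a margin chosen after the results are seen cannot support a confirmatory claim. Loose wording in both the hypothesis and the primary objective still has to be corrected; if that is all it is, rewording is a complete repair. The figures do not establish a sample-size shortfall. They are also favourable in two respects: equivalence power is computed at a true difference of exactly zero, and correlations below 0.5 are not shown. Lower correlations are plausible because the POMS asks about the present moment and is given weeks apart, and they would widen the intervals.

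**Conclusion.** The concern holds and must be fixed. Followed exactly, the plan cannot validly answer its own primary question, because it pairs an equivalence objective with a difference test and has no criterion for equivalence. That conclusion needs no assumed figure.

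The size of the risk does depend on assumptions about SD, correlation, margin and analysed numbers. With 50 per arm and correlations of 0.5 to 0.7, a true 0.5 SD difference would pass as non-significant in 8–28% of trials and a 0.3 SD difference in 50–68%. Whether 50 per arm is adequate for equivalence depends on the margin, the correlation and the both-times rule, none of which the plan states.

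**What to change.** Do one of the following before outcome data are examined.

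**(a) Keep equivalence.**
- Pre-specify and justify a margin in TMD points.
- Estimate the baseline-adjusted between-arm TMD difference at T2 and at T3. This departs from the difference scores under Primary outcomes, so say so; change scores could be used instead, at the cost of wider intervals at these correlations.
- Claim equivalence only if the 90% confidence interval lies inside the margin, and state whether both times are required. Requiring both is suggested and needs no split of alpha.
- Report the result in all randomised participants with data as well as in the adherent set.
- State that a non-significant ANOVA does not show equivalence.
- Restate the power as equivalence power on TMD for the chosen margin over a range of correlations.
- Reword the hypothesis for sleep, stress and immediate effects as comparisons, since a TMD margin does not cover them.

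**(b) If no margin can be justified,** replace *equivalent* with *compare* in sections 3(a) and 3(e), report the between-arm TMD difference at each time with its 95% confidence interval, and make no equivalence claim.

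Neither option adds visits or measurements. Under (a) the claim is harder to win, the restated power may fall below 90%, and more participants may be needed. Section 4 leaves room for that: "We aim to recruit at least 100 participants, with a minimum of 50 university students". Under (b) the equivalence claim is given up.

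### Repeated measures ANOVA and MANOVA, as normally run, discard the observed 4-week mood score of anyone who misses the 8-week questionnaire; this costs precision and can bias the 4-week comparison

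*Combined protocol and SAP*

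**What the plan says.** The Analysis Plan in Section 6 assigns one method to TMD, VAS and sleep: "Univariate repeated measures ANOVA will be used to examine the effects of the intervention on the overall TMD score from the POMS, VAS scores". For the subscales it says: "Repeated measures MANOVA will be used to examine changes in the POMS subscale scores".

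The data come from three questionnaire occasions and a weekly rating. T1 is completed before randomisation. Section 5 then says: "Participants will be asked to complete the mood and sleep measures again after 4- (T2) and 8-weeks (T3". For VAS it says: "Before and after one session each week, participants will be asked to complete the visual analogue ratings scales". Over four weeks that is four pairs, or eight ratings per scale.

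Under Primary outcomes, Section 6 also says: "Difference scores between baseline (T1) and T2 (4 weeks), and T3 (8 weeks) for the POMS TMD will be calculated". It does not say how these difference scores feed the ANOVA.

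The document gives no missing-data rule, imputation method, expected dropout rate or inflation of the sample size. What it does give is reminders and monitoring (Section 5), course credit or a prize draw (Section 4), and the exclusion of anyone without at least one session in each of the first four weeks (Section 6).

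**The concern.** Classical repeated measures ANOVA needs a full row of visits for each person, and standard software deletes incomplete rows. T3 comes after four weeks of optional use in a fully online study, so some participants will probably answer T2 and not T3. Their 4-week TMD is a primary outcome value that has been observed and would then be thrown away. For the subscales, seven scores at three visits make 21 values per person; a missed T3 discards the 14 already recorded at T1 and T2.

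Two things are at stake. The first is precision, which matters more than usual because Sections 3(a) and 3(e) aim at equivalence: the noisier the contrast, the less a finding of no significant difference tells us. The second is validity. If staying to T3 depends on how people felt, and does so differently by arm, those who remain are no longer comparable.

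**Working it through.** **Inputs from the document.** 50 per group, 1:1; two-sided alpha 0.05; T2 and T3 after a pre-randomisation T1; four weekly VAS pairs.

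**Assumptions.** All missingness rates; correlation 0.5 between visits; d = 0.5 for the plan's unquantified medium effect; no true arm difference in the bias checks.

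**1. The plan's own figure.** Section 6 claims: "This will provide > 90% power". For a two-group contrast, power = Φ(d·√(n/2) − 1.96) = Φ(0.5·√25 − 1.96) = Φ(0.54) = 70.5% (exact t: 69.7%). More than 90% is reached on a within-group reading (standardised paired change 0.5, n = 50: 93.4%) or a group-by-time reading (f = 0.25, three visits, correlation 0.3 to 0.7: over 99%). Every one of these uses the full 50 per group, so none allows for missing data.

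**2. Precision at 4 weeks.** The variance of an arm difference is proportional to 1/n. If everyone has T2 and a share m misses T3, complete-case analysis multiplies the variance by 1/(1 − m):

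| T3 missing | 1/(1 − m) | Simulated |
|---|---|---|
| 10% | 1.11 | 1.11 |
| 20% | 1.25 | 1.26 |
| 30% | 1.43 | 1.41 |

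A mixed case: 10% miss T2 and 25% of the rest miss T3. T2 is observed in 100 × 0.90 = 90 people; 90 × 0.75 = 67.5 are complete. With correlation 0.5, the SD of change is √(2(1 − 0.5)) = 1. The SE is √(2/45) = 0.21 SD using every T2 value and √(2/33.75) = 0.24 SD in complete cases. The variance ratio is 90/67.5 = 1.33; simulation gave about 1.34.

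**3. The same loss as power.** With independent missingness p per occasion, the number per arm is 50(1 − p) using all T2 values and 50(1 − p)² in complete cases. Power is for the two-group contrast at d = 0.5:

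| p | All T2: n per arm, power | Complete cases: n per arm, power |
|---|---|---|
| 5% | 47.5, 68% | 45.1, 66% |
| 10% | 45, 66% | 40.5, 61% |
| 20% | 40, 61% | 32.0, 52% |

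**4. Bias at 4 weeks.** These are simulated complete-case contrasts at T2; the true value is 0:

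- T3 missing without regard to outcome: about 0.
- T3 missing depends on the T2 score in the same way in both arms: about 0.
- Dependence in one arm only, 10% loss, log-odds 0.5 per SD: 0.025 SD (depends on T2 score) or 0.05 SD (depends on T2 change).
- Dependence in one arm only, 25% loss, log-odds 1 per SD: 0.11 SD (score) or 0.21 SD (change).

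In these settings the contrast that uses every observed T2 value has bias of about 0.

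**5. VAS, if all four weeks enter as separate occasions.** The share with all four pairs is w⁴ when misses are independent: 0.90⁴ = 66%, 0.85⁴ = 52%, 0.80⁴ = 41%. If misses cluster within people (within-person correlation 0.3 to 0.5, beta-binomial), the shares are 76–81%, 65–72% and 56–64%.

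**The case against.** The best reply is that the primary outcomes are written as separate T1–T2 and T1–T3 differences, and a T1–T2 difference does not need T3. That is so. But the Analysis Plan names repeated measures ANOVA for TMD and never links it to those scores, so loss of the T2 value is the likely reading, not a certain one. The ambiguity is itself a reason to amend the text.

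Three further points stand and limit the concern. The trial has real retention measures, and both arms are self-administered audio tracks of about 10 to 12 minutes on one platform, so nothing in the document points to a strong dropout mechanism in one arm. A person without T2 has no 4-week value under any method; the avoidable loss at 4 weeks comes only from missing T3. And the session-based exclusion already removes anyone who skips a whole week, so part of the attrition cannot be recovered by changing the model.

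A reader might infer that a missed VAS pair removes someone from the TMD or sleep analysis. It does not: deletion works within each outcome's own analysis. Even for VAS it depends on the four weeks entering separately, whereas averaging them would fit the text equally well.

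**Conclusion.** The concern holds as a matter of method. The named analyses, as normally run, waste observed 4-week primary data, and nothing in the plan prevents it. The cost in precision follows directly from the number lost: about 10% to 40% more variance for 10% to 30% missing T3.

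A reader might go further and conclude that the 4-week comparison is biased. The document does not support that, because it gives no dropout rate or pattern. Bias requires dropout that is related to outcome differently by arm. Where that is assumed in one arm only, with 10% to 25% loss and log-odds of 0.5 to 1 per SD, it is about 0.03 to 0.21 SD; the top value is a severe case, not an expectation. The VAS shares of 66%, 52% and 41% are likewise pessimistic, since they assume independent misses. I am confident about the defect and much less so about its size. It should be corrected before analysis.

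**What to change.** In Section 6:

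- **TMD.** Replace the ANOVA with a likelihood-based mixed model for repeated measures (REML, unstructured covariance) with baseline TMD, arm, visit and arm-by-visit. Use all observed T2 and T3 values in the stated analysis set. Report the SB-minus-PMR contrast with its confidence interval at T2 and at T3, and say how the difference scores relate to this model.
- **Subscales and sleep.** Use the same approach for each POMS subscale, in place of the MANOVA, and for the overall sleep rating.
- **VAS.** Model each post-session rating on its own pre-session rating, arm, week and a participant random effect, using every observed pair.
- **Analysis set.** State which set applies. The one-session-per-week exclusion is a separate issue, and this model neither resolves nor overrides it.
- **Sensitivity.** Add one analysis that departs from missing-at-random.

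The cost is a few sentences, slightly more work in standard software and no new data. There are two downsides: no single multivariate test across the subscales, and reliance on missing-at-random, which the sensitivity analysis can probe.
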